**Name of active substance:**

PBTZ169 Hydrochloride

---

consistency of the results between the two methods of determining mycobacterial count.

Only available measurements are used in efficacy analysis. No missing values are restored. The analysis is based on average values for each measurement point. An additional analysis at the maximum of two measurements is carried out (with the highest number of CFU or MBT DNA copies using agar inoculation and quantitative PCR, respectively).

***Safety analysis***

The MedDRA dictionary is used to code adverse events. The number (percentage) of patients with AEs and the number of AEs are tabulated by system organ class and preferred term as well as by study treatment, severity, and treatment group. Each patient is included within each system organ class and preferred term only once regarding the study treatment and maximum severity.

Laboratory test values and their changes from baseline (at screening) following the administration of the study drug and "shift tables" based on reference values are tabulated by treatment groups and measurement points.

The findings of ECG, vital sign assessment, and body temperature measurements are tabulated by study group for each measurement point, including changes from the most recent measurement made prior to dosing.

Physical examination findings are presented descriptively by treatment group and measurement point.

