**Diagnosis and key inclusion criteria:**

Subjects complying with all of the following criteria will be included into the clinical study:

1. Written informed consent received from the subject.
2. Men and women aged 18 to 45 years old, inclusive.
3. Newly diagnosed active pulmonary tuberculosis confirmed by characteristic radiological findings (infiltration, dissemination, and destruction) in chest X-ray or computed tomography not involving other

**Name of active substance:**PBTZ169 Hydrochloride

---

organs or involving one or more of the following: the larynx, the trachea, the bronchi, and lymph nodes.

4. The patient's sputum volume must be enough for any tests provided for under the Protocol but not less than 4 to 5 mL at screening.
5. Acid-fast mycobacteria found in sputum smear microscopy (1+ and more using the luminescent dye microscopy according to Order of the Russian Ministry of Health No. 109 dated March 21, 2003, latest revision) and tuberculosis mycobacterial DNA found in molecular genetic tests.
6. A body weight of at least 51 kg.
7. Body mass index of 18.5–25 kg/m^2.
8. The ability (according to the investigator's opinion) to comply with all requirements of the Protocol.
9. Agreement to use reliable contraception methods during the study and 3 months after the last dose of the drug, including temporary abstinence from sex or double contraception combining male condoms with at least one of the following:
  - Using hormonal contraception
  - Using aerosols, creams, suppositories, and other agents containing spermicides
  - Using an intrauterine device

Subjects who meet any of the following criteria will not be included in the clinical study:

1. Extrapulmonary localization of tuberculosis.
2. Resistance to rifampicin and/or isoniazid found in molecular -genetic tests on sputum samples.
3. Administration of any antituberculosis drugs from the moment of tuberculosis diagnosis to enrolment in the study.
4. Absolute indications for surgical treatment of tuberculosis at screening.
5. Testing positive for syphilis or HIV infection serological markers at screening, active hepatitis, or decompensated liver cirrhosis.
6. History of allergic reactions.
7. Laboratory renal and/or hepatic parameters measured as follows (with due regard to the laboratory's reference range):
  - AST > 2.0 x upper limit of normal values (ULN)

**Name of active substance:**PBTZ169 Hydrochloride

---

---

- ALT > 2.0 x ULN
  - Total bilirubin > 1.5 x ULN

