  - Creatinine > 1.5 x ULN
8. Individual intolerance to any ingredients of the study drug.
  9. History of malignant tumors, except for basal cell carcinoma.
  10. Decompensated severe chronic somatic diseases, including cardiovascular, bronchopulmonary, neuroendocrine, ENT, -gastrointestinal, hepatic, renal, blood, skin diseases, and other somatic or mental diseases that the investigator believes to prevent the subject's enrolment.
  11. Gastrointestinal- surgery (except for appendectomy performed more than 1 year before the screening).
  12. Any mental disorders that can affect the patient's compliance with the Protocol.
  13. Diabetes mellitus.
  14. Acute viral and bacterial infections at enrolment or within 2 weeks prior to enrolment.
  15. Alcoholism (unless the investigator believes the subject to be able to abstain from alcohol consumption during the study) or substance abuse.
  16. A positive test for narcotic and psychotropic products.
  17. Regular administration (including topical) of any hormonal drugs for over 1 week within 30 days before the screening (except for oral hormonal contraceptives and hormonal intrauterine devices).
  18. Use of cytotoxic drugs within 30 days before the screening.
  19. Repeated administration of any drugs where the instruction for medical use mentions nervous system, hemodynamics, and liver function adverse events as "very frequent" ( $\geq 10\%$ ) or "frequent" ( $\geq 1\%$  and  $< 10\%$ ) within 21 days before the screening.
  20. Pregnancy or lactation.
  21. Planned conception or sperm donation during the study after the study drug administration or within 3 months after the date of the last drug administration.
  22. Participation in other clinical trials of drugs within less than 3 months before the screening.

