**Statistical methods:**

Descriptive statistics will be provided for all demographics and other baseline characteristics, efficacy and safety parameters, and changes in them (if applicable) in the course of the study by means of assessment time points and treatment groups. Descriptive statistics for quantitative variables include mean value, standard deviation (SD), minimum and maximum values, and the number of valid observations. Qualitative data is presented as rates and percentages. 95% confidence intervals around point estimations are provided as well (where applicable).

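### Shift tables based on reference values would not count or grade laboratory worsening by dose group, least of all in patients admitted above the upper limit of normal

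*Combined protocol and SAP*

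**What the plan says.** All references are to the synopsis in the combined protocol and SAP.

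- **Safety analysis** plans two laboratory displays in one sentence. One covers "Laboratory test values and their changes from baseline (at screening) following the administration of the study drug". The other display is a set of tables of shifts between categories, which the plan describes as "based on reference values are tabulated by treatment groups and measurement points". The available text does not say how many shift categories there are, and it names no multiple of ULN and no toxicity grade.
- **Statistical methods** gives the summaries for quantitative variables, safety parameters and their changes included: "mean value, standard deviation (SD), minimum and maximum values, and the number of valid observations".
- **Exclusion criterion 7** (under Diagnosis and key inclusion criteria) keeps patients out only above these limits: "AST > 2.0 x upper limit of normal values (ULN", the same multiple for ALT, "Total bilirubin > 1.5 x ULN" and "Creatinine > 1.5 x ULN". The limits apply "with due regard to the laboratory's reference range".
- **Safety analysis** also tabulates adverse events. Each patient counts once per system organ class and preferred term, at maximum severity.

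**The concern.** A shift table is the usual place to read how many patients on each dose moved from an acceptable laboratory value to an abnormal one. Here the table appears to be cut at the edge of the reference range, while the entry limits lie above that edge. A patient may start in the high category and then has no further category to move to. For patients who start in range, a trivial excess and a large one fall in the same cell. Because the tables are made separately for each measurement point, they also do not yield the number of patients who were ever elevated after dosing.

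Safety at 160, 320 and 640 mg is one of the trial's stated goals, and laboratory results are a listed safety variable. With 15 patients planned per dose group, the most informative result is a plain count: how many patients on each dose reached a given degree of elevation.

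**Working it through.** The plan has no figure of its own to reproduce on this point. The check has four steps.

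**1. Can a patient enter above ULN?** Yes. Criterion 7 admits values above 1 and up to 2.0 x ULN for AST and ALT, and above 1 and up to 1.5 x ULN for total bilirubin and creatinine.

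**2. What would the shift table record?** Assume one above-range category. The example ALT values, in multiples of ULN, are illustrations within the entry limits. The last column uses illustrative bands of <=1, >1-2, >2-3, >3-5 and >5.

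| Baseline | Post-dose | Reference-range cell | Change | Cell in ULN bands |
|---|---|---|---|---|
| 0.8 | 1.1 | normal to high | +0.3 | <=1 to >1-2 |
| 0.8 | 4.0 | normal to high | +3.2 | <=1 to >3-5 |
| 1.8 | 1.9 | high to high | +0.1 | >1-2, unchanged |
| 1.1 | 4.0 | high to high | +2.9 | >1-2 to >3-5 |
| 1.8 | 5.5 | high to high | +3.7 | >1-2 to >5 |

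Rows 1 and 2 share a cell although the rises differ about tenfold (3.2/0.3 = 10.7). Rows 3 to 5 share a cell that reads as no shift.

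**3. What do the other summaries recover?** The rise from 1.8 to 5.5 appears in the change table. It adds 3.7/15 = 0.25 x ULN to the mean change of a group of 15, and would normally be that group's maximum. It is therefore visible.

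The number of patients affected is not recovered. Take 15 patients, all at 0.8 x ULN at baseline, and two measurement points at each of which exactly one patient is at 4.0 and the rest are at 0.8. At each point the mean is (14 x 0.8 + 4.0)/15 = 1.01, the maximum is 4.0, the mean change is 3.2/15 = 0.21, and one patient is normal to high. These results are the same whether it is one patient both times (1/15 = 6.7% ever elevated) or two different patients (2/15 = 13.3%).

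**4. How often would a group contain a patient who enters above ULN?** The documents do not give the share p, so it is an assumption. With n = 15 independent patients, the expected number is 15p and the chance of at least one is 1 - (1 - p)^15.

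| Assumed p | Expected per 15 | Chance of at least one |
|---|---|---|
| 5% | 0.75 | 1 - 0.95^15 = 54% |
| 10% | 1.5 | 1 - 0.90^15 = 79% |
| 20% | 3.0 | 1 - 0.80^15 = 96% |

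**The case against.** The strongest reply is that the shift table is only one of several displays. The same sentence plans values and changes from screening, Statistical methods adds the minimum and maximum, and the AE tables count each patient once at maximum severity. A large rise would show in at least the first of these. That stands, and it defeats a reading that a reader might infer: that a dose could produce marked elevations which the trial would fail to report. The documents do not support that reading.

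The reply does not settle counting and grading. Maxima by measurement point do not give numbers of patients (step 3). The AE tables pick up a laboratory rise only if it is reported as an AE, and the available text has no rule saying when it must be. The synopsis numbers its study centers up to 13. If laboratories are local, which is not stated, pooled raw values would not correspond to a common multiple of ULN.

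Three further objections have weight:

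- **Undefined categories.** Low/normal/high is an inference. Bands in multiples of ULN would also fit the words, and a synopsis often leaves such detail out. If finer bands are intended, the remedy is to say so.
- **Liver risk.** A reader might take exclusion criteria 7 and 19 as naming liver injury as a PBTZ169 risk. They do not: criterion 7 is an entry limit, and criterion 19 concerns earlier use of other drugs.
- **Banding.** Any banded table has blind spots. A rise from 1.05 to 2.0 x ULN stays within one band, while 1.95 to 2.05 crosses a boundary. The continuous summaries should therefore stay.

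**Conclusion.** The point holds as a limit on one safety display. If the shift table has a single above-range category, it cannot show further worsening in patients who enter above ULN, cannot grade rises in the others, and gives no count of patients by worst post-dose level. The rises themselves remain visible in the change-from-baseline summaries, and in the AE tables where reported as AEs.

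The size depends on the share entering above ULN, which is unknown. At 5% to 20%, a full group of 15 has a 54% to 96% chance of at least one such patient. The Pharmacokinetic and pharmacodynamic analysis section says the study was terminated early, so actual groups may be smaller, with a lower chance of including such a patient but a larger fraction of the group for each one. The lack of grading and of patient counts does not depend on that share.

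The primary endpoint, the sample size and the significance level are unaffected. The change is still worth making, because safety by dose is a stated goal and the better display costs very little.

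**What to change.** Keep the reference-range shift tables and state their categories. For ALT, AST, total bilirubin and creatinine, add one shift table each by treatment group, specified as follows:

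- **Baseline:** the plan's own, which is screening, or the last pre-dose value if one is collected. State which.
- **Post-dose value:** each patient's worst value over monotherapy and the 7-day follow-up, so that late elevations are included.
- **Scale:** multiples of the ULN of the laboratory that tested the sample.
- **Bands:** pre-specified. The first two are <=1 x ULN, and >1 x ULN up to the trial's entry limit (2.0 for ALT and AST, 1.5 for bilirubin and creatinine), with graded bands above that. The documents give no cut-points above the entry limits. For ALT and AST, >2-3, >3-5 and >5 would be one illustration.
- **Report:** the number of patients in each band and the number moving above the entry limit.

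The cost is a few lines of SAP text and four extra descriptive tables, with no new visits, tests or patients. The downside is small cell counts at 15 per group. The tables support description only, with no formal inference.

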**Name of active substance:**

PBTZ169 Hydrochloride

---

Nocturnal sputum is collected from all subjects in the morning at V1. After that, every patient received the study drug (PBTZ169 or isoniazid) as a monotherapy for 14 consecutive days. After 14 days of monotherapy (Day 15 of the study, V8), PBTZ169 is discontinued in Groups 1 to 3 (Day 14 being the day of the last PBTZ169 dose). Standard therapy is initiated 3 days after the monotherapy end date (Day 18 of the study, V10). Standard therapy drugs are resumed in Group 4 (standard dose of isoniazid) without a break—that is, the day following the monotherapy end date (Day 15 of the study). Patient monitoring during clinical study is continued on a hospital basis and ended 7 days following the monotherapy end date.

Venous blood samples are taken from all subjects in Groups 1, 2, and 3 (PBTZ169 monotherapy) to measure PBTZ169 levels. Blood samples are drawn before the first dose of PBTZ169 (0 min time point) and later at the following time points after the first dose: in 0:20, 0:40, 1:00, 1:30, 2:00, 2:30, 3:00, 4:00, 6:00, 8:00, 10:00, 12:00, and 24:00 (hr:min). Blood samples are also taken before the last dose of PBTZ169 (0 min time point) and later at the following time points after the last dose: after 0:20, 0:40, 1:00, 1:30, 2:00, 2:30, 3:00, 4:00, 6:00, 8:00, 10:00, 12:00, 24:00, 48:00, and 72:00 (hr:min).

All venous blood samples are kept in case any additional parameters have to be measured.

Subjects are hospitalized throughout the monotherapy and follow-up periods.

**Number of subjects:** It's planned to randomize 52 eligible subjects for the study, namely 15 subjects in each PBTZ169 group and 7 subjects in the isoniazid group.

The data of subjects who will receive at least one dose of the study drug and whose study drug concentrations are known will be processed in the final statistical analysis of efficacy and pharmacokinetics.

The data of subjects of ITT population will be processed in the final statistical analysis of safety.

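### Laboratory, ECG and vital-sign results are summarised by measurement point only, in every group, so the plan gives no count of patients abnormal at any time on monotherapy unless the abnormality is also recorded as an adverse event.

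*Combined protocol and SAP*

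**What the plan says.** Safety is one of the stated goals of the study. The Safety list under Assessment parameters names adverse events, vital signs, laboratory tests, ECG and physical examination.

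The general rule under Statistical methods is that safety parameters and their changes are described "in the course of the study by means of assessment time points and treatment groups". The statistics are fixed there too: "Descriptive statistics for quantitative variables include mean value, standard deviation (SD), minimum and maximum values, and the number of valid observations".

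The Safety analysis section applies this rule to each type of objective data:

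- **Laboratory:** values, changes from screening, and shift tables "based on reference values are tabulated by treatment groups and measurement points".
- **ECG, vital signs and temperature:** "tabulated by study group for each measurement point, including changes from the most recent measurement made prior to dosing".
- **Physical examination:** "Physical examination findings are presented descriptively by treatment group and measurement point".

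Adverse events are treated differently: "Each patient is included within each system organ class and preferred term only once regarding the study treatment and maximum severity".

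On numbers, 52 patients are planned, "namely 15 subjects in each PBTZ169 group and 7 subjects in the isoniazid group". On the population: "The data of subjects of ITT population will be processed in the final statistical analysis of safety".

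**The concern.** The plan counts across time within a patient for adverse events but not for the objective safety measurements. If one patient in a dose group has a raised transaminase at one visit and one patient has it at the next, the two tables look the same whether this is one person or two. No choice of shift categories or baseline value changes that. The minimum and maximum do not help either: they show how extreme a value was at a visit, not how many different people had one.

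In a 14-day, three-dose study with small groups, the number of patients with an abnormality at any time during dosing is a basic safety result. If abnormalities are transient and fall in different patients, a dose-related liver or ECG signal could appear as one isolated case at each visit.

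The adverse event table closes the gap only in part. The text available for this review has no rule that makes a laboratory or ECG abnormality an adverse event. Such a finding enters that table only if the investigator, who is unblinded in this open-label study, reports it.

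**Working it through.** **Inputs from the documents.** Planned group sizes are 15, 15, 15 and 7 (Number of subjects). The stated total reproduces: 3 × 15 + 7 = 52. The sample size is described as empirical, so there is no power calculation to check. No abnormality rate is stated for any safety parameter.

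**Assumed inputs.** The number of on-treatment measurement points, k, is not in the available text. I use 3 and 4 as the main illustration and show 1 to 6. I also assume one abnormal patient at each point, and all N patients measured each time.

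**Formula.** Let a_j be the number of abnormal patients at point j, and E the number abnormal at least once. The tables by measurement point fix only the bounds

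max(a_j) ≤ E ≤ min(N, Σ a_j).

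The lower bound is reached when the same patients are abnormal throughout, and the upper bound when they are all different. If occurrence were independent from point to point with probability p = 1/15, the expected share ever affected would be 1 − (1 − p)^k = 1 − (14/15)^k.

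**One PBTZ169 group, N = 15, one abnormal patient at each point:**

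| k (assumed) | Shown at each point | Same patient | Independent | All different |
|---|---|---|---|---|
| 1 | 6.7% | 6.7% | 6.7% | 1/15 = 6.7% |
| 2 | 6.7% | 6.7% | 1 − (14/15)² = 12.9% | 2/15 = 13.3% |
| 3 | 6.7% | 6.7% | 1 − (14/15)³ = 18.7% | 3/15 = 20.0% |
| 4 | 6.7% | 6.7% | 1 − (14/15)⁴ = 24.1% | 4/15 = 26.7% |
| 6 | 6.7% | 6.7% | 1 − (14/15)⁶ = 33.9% | 6/15 = 40.0% |

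**Isoniazid group, N = 7.** One abnormal patient at each point shows as 1/7 = 14.3%. The share ever affected lies between 14.3% and 3/7 = 42.9% for k = 3, or 4/7 = 57.1% for k = 4. The ambiguity is therefore common to all groups.

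**Reading.** Within a row, the planned tables by measurement point are the same in all three scenarios. They cannot separate 1 patient in 15 from 3 or 4 in 15.

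**Check on the time window for a patient-level count.** The Design section first gives Group 4 isoniazid alone for 4 days. Later text in the same part of the synopsis, and Comparator treatment duration, give 14 days. On the 14-day description, Group 4 moves to standard therapy on Day 15, whereas the PBTZ169 groups start it on Day 18 after three drug-free days (Days 15 to 17). A window through Day 15 is therefore not known to be free of standard therapy in Group 4.

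**The case against.** The strongest reply is that nothing in the plan is wrong as stated. It defines no ever-abnormal endpoint, and its summaries match the safety variables it lists. Extremes are not hidden, because the maximum and the shift tables at each visit would show a transient high value. The adverse event table counts patients once across the study. Only synopsis-level text was available, so fuller rules may exist elsewhere. The rates and visit numbers above are invented, and the study was terminated early, so 15 may not be the real denominator.

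Much of this stands, and it limits the point. A reader might infer that the share of patients ever affected is understated. The documents do not support that: no such share is reported, so none is understated. A reader would go wrong only by taking one visit's percentage as cumulative, and only if different patients were affected at different visits. A reader might also infer that abnormalities are never added up, or that the layout favours PBTZ169. Neither holds: abnormalities recorded as adverse events are accumulated, and the same layout applies to isoniazid.

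What does not stand is that maxima and shift tables by visit fill the gap. They show that an abnormality occurred, not how many patients had one. Patient listings could, but the available text mentions listings only for drug concentrations. Early termination does not remove the need either: in smaller groups each affected patient weighs more.

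Two objections to the remedy also need an answer. The multiples of the upper limit of normal in exclusion criterion 7 are eligibility limits, not on-treatment safety thresholds, so they can serve only as descriptive cut-offs. For ECG and vital signs the available text gives no abnormality limits. The largest change per patient is therefore a patient-level summary but not a count of affected patients.

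**Conclusion.** The point holds as a gap in reporting, not as a bias. As described in the available text, laboratory, ECG and vital-sign results are summarised by measurement point only, in all groups. Except for abnormalities also recorded as adverse events, the number of patients abnormal at any time on monotherapy is not given and cannot be recovered from the described tables.

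The size is illustrative. It rests on the planned 15 per group, complete measurements, one abnormal patient per visit and an assumed number of visits. The gap is zero with a single on-treatment measurement or if the same patient is abnormal throughout. The real gap cannot be computed from the documents.

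No primary or secondary efficacy result is touched. The change is worth making because it serves a stated goal at little cost.

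**What to change.** In the Safety analysis section, keep the tables by measurement point and add the following by treatment group:

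- **(a)** For each laboratory parameter, a shift table from baseline to the worst value after the first dose, counting each patient once.
- **(b)** n/N (%) of patients with at least one value outside the reference range already used for the shift tables, and n/N (%) above the limits in exclusion criterion 7 (2.0 × ULN for AST and ALT, 1.5 × ULN for total bilirubin and creatinine). State that these limits are descriptive reporting cut-offs only. Eligible patients were not above them at screening, which is the laboratory baseline, so any later exceedance is new.
- **(c)** For ECG and vital signs, the largest change per patient from the last pre-dose value.

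Define the window as the first dose to the last assessment before the first dose of standard therapy. Show the drug-free days after the last PBTZ169 dose separately, so that the main window is comparable with isoniazid and later abnormalities are not lost. The statements on Group 4 monotherapy length (4 days in one place, 14 days in others) must be reconciled before that group's window is fixed.

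The cost is a few sentences and a few tables from data already collected, with no extra samples or patients. The downside is that the reported abnormality rates may look slightly less favourable.
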